**Table 6: Pharmacokinetic sampling time per Protocol and for analysis**

	Nominal time (Analysis time point)		Time window
	(h)	(min)	(min)
Predose	0	0	Before dosing at the visit
Postdose	3	180	96 - 288

The plasma BDQ, M2, CAM and 14-OH-CAM concentrations will be tabulated and summarized by intervention group, respectively. Individual concentrations will be listed.

#### 5.7.1.2. Population Pharmacokinetic Analysis

Population PK (popPK) analysis of plasma concentration-time data of BDQ (and M2, if needed) will be performed with nonlinear mixed-effects modeling (NONMEM) approach. If deemed necessary, data will be combined with data from other studies. Details will be given in a population PK analysis plan and the result will be presented in a separate report.

In the popPK analysis, based on the individual plasma concentration-time data, using the actual dose taken and the actual sampling times, PK parameters ( $C_{max}$ ,  $C_{trough}$  [trough concentration],  $AUC\tau$ ) of BDQ at Day 1, Weeks 2, 8, 12, 24, and 48 will be derived. If deemed necessary, a similar analysis for  $C_{max}$ ,  $C_{trough}$ ,  $AUC\tau$  will be performed for M2.

Descriptive statistics (N, mean, standard deviation, %CV, median, minimum and maximum) will be calculated to summarize PK parameters of TMC207 (and M2, if needed) at Day 1, Weeks 2, 8, 12, 24, and 48.

For descriptive statistics of the PK parameters of BDQ (and M2, if needed) from population pharmacokinetics, following parameters will be reported.

- $C_{\max}$ ,  $C_{\text{trough}}$  and  $AUC_{\tau}$

The PK parameters of BDQ (and M2, if needed) will be tabulated and summarized at Day 1, Weeks 2, 8, 12, 24, and 48, respectively.

### 5.7.1.3. Generating Pharmacokinetic Profiles

The following graphs will be produced by intervention group:

- Boxplots of the BDQ concentration at predose and 3 hours postdose (Day 1, Weeks 2, 8, 12, 24, and 48), respectively.
- Boxplots of the M2 concentration at predose and 3 hours postdose (Day 1, Weeks 2, 8, 12, 24, and 48), respectively.
- Boxplots of the CAM concentration at predose and 3 hours postdose (Day 1, Weeks 2, 8, 12 and 24), respectively.
- Boxplots of the 14-OH-CAM concentration at predose and 3 hours postdose (Day 1, Weeks 2, 8, 12 and 24), respectively.

### 5.7.2. Pharmacokinetic/Pharmacodynamic Relationships

PK/PD analyses will be performed on the collected data when all participants have reached Week 24 or discontinued earlier. The PK/PD analyses may be performed at earlier time points as necessary to support efficacy and safety findings.

The PK/PD analysis will be based on the PK/PD analysis set (defined in Section 4) for nominal time-matched plasma concentrations and safety parameters.

Safety parameter: QTcF

- 3 hours postdose at each visit on Day 1, Weeks 2, 8, 12, 24, and 48

The following plots will be generated to evaluate the relationship between safety parameter (absolute value and change from baseline for QTcF) and plasma concentrations of BDQ, M2, CAM and 14-OH-CAM, respectively:

- QTcF at each time-matched point of measurement from each intervention group (for BDQ, and M2, Treatment A only) will be plotted against the corresponding plasma concentration of BDQ, M2, CAM and 14-OH-CAM, respectively.
- Additional plots will be produced, if deemed necessary.

Pearson product moment correlations ( $R^2$ ) will be calculated for nominal time-matched plasma concentrations and safety parameter.

Population PK/PD (selected efficacy endpoints and selected AEs as additional PD parameters) analysis may be evaluated. If there is any visual trend in graphical analysis, suitable models will be applied to describe the PK/PD relationships. Details will be given in a PK/PD analysis plan will be presented in a separate report.

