## Footnotes:

- a. Screening evaluations must be performed within 70 days (10 weeks) prior to baseline (Day 1). These 10 weeks include 14 days of rifamycin W/O for participants to whom it is applicable. If screening period exceeds 10 weeks for reasons such as time required to obtain the result of microbiology assessment of screening, the screening period may be extended up to 15 weeks.
- b. If required during the 48-week treatment period, participants can have a change in their treatment regimen, in which MAC-LD treatment may continue in accordance with standard of care or NTM treatment guidelines. All decisions on treatment regimen change should be made based on clinical worsening supported by microbiology data by the investigator. Participants requiring a treatment regimen change will be followed up for safety only, but all assessments should be performed according to the protocol.
- c. Assessments planned on Day 1 except for blood sampling for PK which is performed after dosing must generally be performed prior to first dose of study intervention.
- d. Every 4-week visit must be scheduled after more than 25 days from the previous visit.
- e. The participants who have been treated with BDQ-containing regimen (Group A) through Week 48 and culture converted, will transfer to the follow-up period. The participants who have been treated with rifamycin-containing regimen (Group B) through Week 48 will continue to be treated up to Week 60.
- f. Early discontinuation visit is to be scheduled within 7 days of the investigator's discretion to discontinue treatment with study intervention (including the day of discontinuation, other than withdrawal of consent). Visit for switch to individualized treatment regimen is to be scheduled within 7 days after discontinuing the assigned treatment regimen (including the day of switch) and before the start of individualized treatment regimen.
- g. Must be signed before first study-related activity.
- h. Investigators should ensure that all study enrollment criteria have been met at screening. If a participant's clinical status changes (including any available laboratory results or receipt of additional medical records) after screening but before the first dose of study intervention is given such that he or she no longer meets all eligibility criteria, then the participant should be excluded from participation in the study.
- i. Medical and surgical history, including NTM exposure history, NTM treatment history, and MAC-LD.

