- q. In case of recurrence (relapse/reinfection) or in case of acquired resistance (at least 4-fold increased MIC) to BDQ is indicated by DST result, baseline and postbaseline isolates will be identified using WGS or VNTR if necessary. If more than 1 postbaseline positive culture (isolate) showing resistant is available the last culture positive sample will be tested for VNTR and/or WGS in addition to the baseline culture positive sample.
- r. Lung function test on Day 1 will be acceptable within 1 week prior to Day 1.
- s. Chest CT scans taken within 6 months prior to screening are acceptable.
- t. Single sparse blood samples will be collected for measurement of plasma concentrations of BDQ (and M2 [optional]). These samples can be taken at any time after intake of BDQ on the day, but the date and time of the second to last and the last administration of BDQ and CAM, respectively, and the date and time of blood draw must be recorded.
- u. Two blood samples will be drawn: one just before intake of BDQ or first intake of CAM in the visit, and the second sample between 2 to 4 hours after the intake. The date and time of the last study drug administrations of BDQ and CAM, respectively, prior to the first PK samples and the date and time of the study drug administrations immediately after the first PK samples must be recorded. The date and time of the blood draw must be recorded.
- v. Extra visits will be required for participants meeting certain grading thresholds for changes in QTcF. All ECGs will be performed in triplicate (3 ECGs within 5 minutes) and must be of good quality (stable baseline, free of interference and artefact). The ECG machine dedicated for this study must be used. All tracings will be transmitted for blinded central analysis. ECG at 2-4 hours post-dose of BDQ and CAM will be obtained at Week 2, Week 12, Week 24 and Week 48. ECG at pre-dose of BDQ and CAM will be obtained at Day 1, Week 4, Week 6, Week 8, Week 16 and Week 32. Those ECG should be performed within 20 minutes prior to PK blood sampling at every time point whenever possible. ECG will be performed before blood sampling at the other visit where time points of ECG measurement are not specified.

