### **QTcF Prolongation**

If a single ECG shows QTcF  $\geq 500$  ms or an increase from baseline (mean of triplicates on Day 1) of  $>60$  ms, then complete additional triplicate ECGs, evaluate the mean QTcF, and record results on an unscheduled visit form.

If triplicate ECGs confirm a mean QTcF  $\geq 500$  ms or an increase from baseline of  $>60$  ms, the following will be done:

- the investigator must assess potential causes of the abnormality including at a minimum a check and correction of electrolyte imbalances ( $K^+$ ,  $Mg^{+2}$ ,  $Ca^{+2}$ ), review and adjust combination medications as necessary (eg, temporarily discontinuation of BDQ and CAM), and obtain weekly duplicate/triplicate ECGs until resolution,
- if after 2 weeks mean QTcF is  $\geq 500$  ms or increase from baseline of  $>60$  ms, the investigator must permanently stop the study intervention, and continue weekly triplicate ECGs until resolution.

Weekly triplicate ECG monitoring for participants who have recovered from QTcF  $\geq 500$  ms or increase from baseline of  $>60$  ms may be discontinued if over 3 consecutive weeks the triplicate ECGs demonstrate a mean QTcF  $<500$  ms or one time increase of  $\leq 60$  ms. Participants who meet these criteria can be switched to less frequent ECG monitoring per Section 1.3, [Schedule of Activities \(SoA\)](#). If mean QTcF  $<500$  ms or increase of  $\leq 60$  ms is not demonstrated, then weekly triplicate ECGs will be continued at least until the end of the last dose of BDQ plus 4 weeks due to the long half-life of BDQ. At that point, if mean QTcF  $<500$  ms or increase of  $\leq 60$  ms is demonstrated, weekly triplicate ECGs can be switched to less frequent ECG monitoring per Section 1.3, [Schedule of Activities \(SoA\)](#). Otherwise if mean QTcF  $<500$  ms or increase of  $\leq 60$  ms is not demonstrated, the investigator judges whether weekly triplicate ECGs will be continued or be switched to less frequent ECG monitoring per Section 1.3, [Schedule of Activities \(SoA\)](#).

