### 5.1.1. Visit Windows

As participants do not always adhere to the protocol visit schedule, the following rules are applied to assign actual visits to analysis visits. Listed below are the visit windows and the target days for each visit. The reference day is Study Day 1. If a participant has 2 or more actual visits in 1 visit window, the visit closest to the target day will be used as the protocol visit for that visit window. The other additional visit(s) will not be used in the summaries or analyses but they can be used for determination of clinically important endpoints. If 2 actual visits are equidistant from the target day within a visit window, the later visit is used.

All assignments will be made in chronological order. Once a visit date is assigned to a visit window, it will no longer be used for a later time point except for the endpoint. Listed below (Table 2 and Table 3) are the analysis visit windows and the target days for each visit defined in the protocol.

Start date in the investigation phase is defined as the date of first study intervention intake. All efficacy and safety assessments during the investigation phase will be assigned an analysis study day relative to this date.

The investigation phase study day in the investigation phase (ADY) is defined as:

$$\text{ADY} = \text{visit date} - \text{investigation phase start date} + 1$$

For visits on or after investigation phase Day 1, and

$$\text{ADY} = \text{visit date} - \text{investigation phase start date}$$

For visit before investigation phase Day 1 (screening phase).

The optional investigation phase study day in the optional investigation phase (ADY) is defined as:

$$\text{ADY} = \text{visit date} - \text{optional investigation phase start date} + 1$$

For visits on or after optional investigation phase Day 1.

All efficacy and safety assessments during the Follow-up (FU) phase will be assigned a day relative to FU start date. The FU study day in the FU treatment phase (ADY) is defined as:

$$\text{FU ADY} = \text{visit date} - \text{FU start date} + 1$$

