### 5.6.3.3. Electrocardiogram

The ECG parameters that will be analyzed are heart rate, PR interval, RR interval, QRS interval, QT interval, and corrected QT (QTc) interval using the correction method, Bazett's formula (QTcB), Fridericia's formula (QTcF).

Bazett's formula:  $QTcB \text{ (msec)} = QT \text{ (msec)} / (RR \text{ (msec)}/1000)^{1/2}$ ; if RR is missing, use  $QT \text{ (msec)} * (HR(bpm)/60)^{1/2}$

Fridericia's formula:  $QTcF \text{ (msec)} = QT \text{ (msec)} / (RR \text{ (msec)}/1000)^{1/3}$ ; if RR is missing, use  $QT \text{ (msec)} * (HR(bpm)/60)^{1/3}$ .

For the time points on which triplicate ECGs apply, a rounded mean value to the nearest integer per triplet will be calculated per time point before any further handling. This round mean value will be used through the entire analysis also in case of 1 or 2 missing values.

ECG records with partial dates (any of day/month/year is missing) will not be used in analysis except in the listings.

If heart rate (HR) is missing, it will be calculated using RR (if available) and rounded to the integer value (see the formula below) before any further handling if applicable.

$$\frac{1000}{RR(ms)} = \frac{HR(bmp)}{60}$$

HR from the vital signs section (ie, pulse) will not be used in this ECG analysis section. RR values (if applicable) will only be listed. Recalculated HR values will be flagged.

The number and percentage of participants with QTc interval will be summarized at each scheduled time point. The number and percentage of participants with QTc interval increases from baseline to the maximum postbaseline value will be summarized. Refer to the following table for summary categories.

Criteria for Abnormal QTc Values and Changes from Baseline	
QTcF/QTcB value	<=450
	>450 – 480
	>480 – 500
	>500
QTcF/ QTcB change from baseline	<=30
	>30 – <=60
	> 60

A shift table will be provided summarizing the shift from baseline to maximum QTc interval classification over time

Descriptive statistics of ECG parameters and change/percent change from baseline will be summarized at each scheduled time point.

If ECG measurements are repeated at a visit, they will be averaged. The averaged value will be considered the 'Visit' ECG result.

Abnormality criteria (based on criteria defined below) will be applied to baseline and postbaseline values.

Postbaseline abnormalities will be compared with their corresponding baseline result:

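### SAP 5.7.2 asks for post-dose QTcF on Day 1 and Week 8, where the protocol schedules only pre-dose ECGs; how confirmatory ECGs enter the QTcF tables is also left open

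*SAP*

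**What the plan says.** **PK/PD analysis.** SAP 5.7.2 bases the concentration-QTcF plots and Pearson correlations on values matched by nominal time. It sets the QTcF time points as "3 hours postdose at each visit on Day 1, Weeks 2, 8, 12, 24, and 48", for BDQ, M2, CAM and 14-OH-CAM.

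**ECG timing.** Footnote v to the protocol's Schedule of Activities says "ECG at 2-4 hours post-dose of BDQ and CAM will be obtained at Week 2, Week 12, Week 24 and Week 48" and "ECG at pre-dose of BDQ and CAM will be obtained at Day 1, Week 4, Week 6, Week 8, Week 16 and Week 32". Footnote c agrees for Day 1: "Assessments planned on Day 1 except for blood sampling for PK which is performed after dosing must generally be performed prior to first dose". Footnote v also asks that these ECGs be taken within 20 minutes before the PK blood draw where possible.

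**PK timing.** Footnote u requires two samples at each marked visit, one just before intake and "the second sample between 2 to 4 hours after the intake". The Schedule marks such pairs for BDQ on Day 1 and Weeks 2, 8, 12, 24 and 48, and for CAM at the same visits except Week 48.

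**Repeat ECGs.** SAP 5.6.3.3 first forms a rounded mean per triplicate, then adds: "If ECG measurements are repeated at a visit, they will be averaged". Protocol 8.2.3 provides that when a single ECG reaches 500 ms, or rises more than 60 ms from baseline, sites "then complete additional triplicate ECGs, evaluate the mean QTcF, and record results on an unscheduled visit form". It is the mean of that additional triplicate that confirms the finding.

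**The concern.** Two of the six QTcF time points named in SAP 5.7.2 have no scheduled ECG of the kind the analysis needs. A programmer working from the SAP alone would look for post-dose QTcF on Day 1 and Week 8 and find none. The plan also leaves out a pair that the protocol does deliver, the Week 8 pre-dose ECG with the pre-dose concentration.

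The second matter is how an ECG taken to confirm a high reading is handled. The SAP does not say whether a confirmatory triplicate recorded on an unscheduled form is a repeat at the same visit, and so averaged in, or a separate visit. Nor does it say whether such a triplicate enters the maximum post-baseline categories.

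QT prolongation is the only entry under study-drug risks in protocol 2.3.1, so its exposure-response description and outlier counts should be reproducible from the plan.

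**Working it through.** **Step 1. Compare the time points.** Inputs: SAP 5.7.2 for the visits wanted; footnote v for ECG timing; the Schedule's PK rows, footnote u and protocol 8.4.3 for the samples.

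| Visit in SAP 5.7.2 | Scheduled ECG | BDQ/M2 post-dose sample | CAM post-dose sample | BDQ/M2 pair | CAM pair |
|---|---|---|---|---|---|
| Day 1 | pre-dose | yes | yes | no | no |
| Week 2 | post-dose | yes | yes | yes | yes |
| Week 8 | pre-dose | yes | yes | no | no |
| Week 12 | post-dose | yes | yes | yes | yes |
| Week 24 | post-dose | yes | yes | yes | yes |
| Week 48 | post-dose | yes | no | yes | no |

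Pairs available: 4/6 = 67% of visits for BDQ and M2, and 3/6 = 50% for CAM and 14-OH-CAM. SAP 5.7.2 times the analysis for when all participants have reached Week 24 or discontinued. Of the five listed visits up to Week 24, three can be paired for every analyte.

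One caution on CAM at Week 48: protocol 8.4.1 does not exclude it in its sampling sentence. The Schedule, protocol 8.4.3 and 9.4.7, and SAP 5.7.1.1 all do, and the count follows those.

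**Step 2. What is collected but unused.** At Week 8 the pre-dose ECG sits beside a pre-dose BDQ and CAM sample, a valid time-matched pair. The Day 1 pre-dose ECG is the baseline (protocol 8.2.3 and 9.4.6), so its change from baseline is zero by construction.

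**Step 3. Effect of averaging a confirmatory triplicate, if it is averaged.** Let m1 be the mean of the triplicate containing the triggering reading and m2 the mean of the additional triplicate. The protocol confirms when m2 >= 500. The visit average exceeds 500 only when (m1 + m2)/2 > 500, that is, m1 > 1000 - m2.

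- Confirmed but not counted: readings 502, 486, 488 give m1 = 1476/3 = 492; readings 501, 504, 503 give m2 = 1508/3 = 502.7, rounded to 503. Average (492 + 503)/2 = 497.5, not above 500.
- Confirmed and counted: m1 = 508, m2 = 502. Average 1010/2 = 505.
- Not confirmed but counted: m1 = 530, m2 = 480. Average 1010/2 = 505.

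When both means exceed 500, so does the average. The classification changes only when the two means lie on opposite sides of 500, or when the average is exactly 500.

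**Step 4. If the confirmatory triplicate is a separate visit instead.** SAP 5.1.1 uses the visit closest to the target day, and "If 2 actual visits are equidistant from the target day within a visit window, the later visit is used". On the same day that keeps the confirmatory triplicate, which preserves a confirmed event. The weekly follow-up ECGs of protocol 8.2.3 can, however, share one window with a scheduled visit (Week 24 covers Days 157 to 184, which is 28 days), and those further from target leave the by-visit summaries.

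**The case against.** The strongest reply is that little harm follows from the plan as written. A reader might infer that the correlation would mix pre-dose QTcF with post-dose concentration. The documents do not support that: SAP 5.7.2 restricts the analysis to values matched by nominal time, and the PK/PD analysis set in SAP 4 requires at least one such pair. Applied literally, the Day 1 and Week 8 cells are empty. The error is an unworkable specification and an unused pair.

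A reader might also infer that averaging hides the QT events that led to treatment action. That goes too far. The SAP does not say that confirmatory triplicates are averaged; only borderline cases would change, and in either direction. Other routes also exist. SAP 5.1.1 lets extra visits serve clinically important endpoints, and SAP 5.6.3.3 uses the maximum post-baseline value for QTc increases and a shift table on maximum QTc class. Listings include unscheduled ECGs, and QT prolongation is an adverse event of special interest. What stands is that none of the table rules says unscheduled ECGs count, whereas SAP 5.3.1 says so expressly for sputum cultures.

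Finally, the SAP's category above 500 ms, set against the protocol's action level of 500 ms or more, might look like a departure. It is not: protocol 9.4.6 itself prespecifies above 500 ms for analysis.

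**Conclusion.** The mismatch holds. SAP 5.7.2 specifies post-dose QTcF at two visits with only pre-dose ECGs scheduled, so the analysis can be done at 4 of 6 visits for BDQ and M2 and 3 of 6 for CAM and 14-OH-CAM. These counts concern scheduled assessments; an unscheduled post-dose ECG could exist for an individual participant.

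The repeat-ECG point is a gap in specification, not a demonstrated undercount. Its effect depends on the confirmatory triplicate being treated as a repeat at the visit, and is then limited to means that straddle 500 ms or average exactly 500. No rate is attached, because the documents give no variability between triplicates.

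Both matters concern safety and exploratory analyses. Neither touches the primary endpoint or any clinical action rule.

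**What to change.** 1. **SAP 5.7.2.** Set the post-dose QTcF time points to Weeks 2, 12, 24 and 48 for BDQ and M2, and Weeks 2, 12 and 24 for CAM and 14-OH-CAM. Add Week 8 pre-dose QTcF paired with pre-dose concentration. State that the Day 1 pre-dose ECG serves as baseline only.
2. **SAP 5.6.3.3.** Keep each triplicate mean as a separate value. Base the maximum post-baseline QTcF value and change categories on all post-baseline triplicate means, scheduled and unscheduled, and say so.
3. **Optional.** Report a count at 500 ms or more beside the prespecified category above 500 ms, so that the table can be read against protocol 8.2.3.

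The cost is SAP wording and derivation code. No new data, visit or change to participant management is needed. Borderline outlier counts may move in either direction.

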## **5.8. Interim Analyses and Data Monitoring Committee (DMC) Review**

### **5.8.1. Interim Analysis**

Interim futility analysis will be conducted at the time when the first 60 randomized subjects have completed Week 24 visit or ended study participation or switched to individualized treatment regimen before Week 24 visit. This futility analysis is nonbinding and the IDMC will recommend the continuation or termination of the study based on the whole package of information, which also includes other efficacy and safety assessments.

The primary analysis will be conducted at the time when all participants have completed Week 24 or discontinued earlier.

After the primary analysis, IAs are planned when:

- All participants have reached Week 48 or discontinued earlier or have switched to the optional cohort
- All participants have reached Week 60 or discontinued earlier or have switched to the optional cohort

The final analysis will be performed when all participants have completed the last study visit or discontinued earlier.

This SAP covers the definitions of analysis sets, derived variables and statistical methods for the primary analysis, interim analyses after the primary analysis and final analyses of this study. For the interim futility analysis, the detailed analysis including the definitions of analysis sets, derived variables and statistical methods are documented in IDMC SAP.

